## **Clinical Study Protocol**

### **Johnson & Johnson Vision Care, Inc.**

provided for ordinal endpoints. For each of the primary endpoints, when there is more than one measurement taken for each subject (eye for WBC), the mean will be used in the analysis and a test based on the corresponding correlation coefficient will be conducted for each of the endpoints separately using two-sided 95% confidence intervals. The relationship of the endpoints will be concluded to be significant if 0 does not fall within confidence limits of the corresponding coefficient. The directional statistical relationship will be determined using the upper or lower limit of the 95% confidence interval. Upper limit below zero or lower limit above zero of the 95% confidence will determine negative or positive relationship, respectively, between the clinical measures.

3. There will be a relationship between change in CLDEQ score between Part 1 and Part 2 and the difference in the (follow-up – baseline) and (follow-up – fitting) values between Part 1 and Part 2 for all clinical measures except density of white blood cells.

Correlation analysis will be conducted for the change in CLDEQ score and the difference in the (follow-up – baseline) and (follow-up – fitting) values of all clinical measures except density of white blood cells between Part 1 and Part 2. Pearson product-moment correlation coefficient will be provided for continuous endpoints. For each of the primary endpoints, when there is more than one measurement taken for each subject, the mean will be used in the analysis and a test based on the corresponding correlation coefficient will be conducted separately. Tests for the relationship each of the endpoints will be conducted separately using two-sided 95% confidence intervals constructed for the corresponding correlation coefficient. The relationship of the endpoints will be concluded to be significant if 0 does not fall within confidence limits of the corresponding coefficient. The directional statistical relationship will be determined using the upper or lower limit of the 95% confidence interval. Upper limit below zero or lower limit above zero of the 95% confidence will determine negative or positive relationship, respectively, between the clinical measures.

4. For Part 1 and 2: at 14 hours, symptomatic subjects will have a greater change from baseline in all the clinical measures except density of white blood cells in the eyelid margins.

The analysis procedure will follow the exact steps for analyzing the change from baseline in mean as described in the primary analysis section for LMS, NIBUT, TMH, and TOSM except the response variable will be the change of LMS, NIBUT, TMH, and TOSM from the corresponding baseline and the covariate baseline LMS, NIBUT, TMH, and TOSM will be excluded from the model. Comparisons between subject strata will be carried out using a one-sided 95% CI of least-square means differences (symptomatic - asymptomatic) for the change from baseline for the hypothesis given below:

$$H_0: \mu_S - \mu_A \leq 0$$
$$H_A: \mu_S - \mu_A > 0,$$

# **Clinical Study Protocol**

## **Johnson & Johnson Vision Care, Inc.**

where S=Symptomatic and A=Asymptomatic. A statistically greater change, on average, for symptomatic subjects compared to asymptomatic subjects will be concluded if the lower limit of the 95% confidence intervals for the Least-squares means is greater than 0.

Other observations will be presented in a separate laboratory protocol and will be analyzed in a separate report.

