### Other Endpoints

Change from baseline and 14 hours and change from fitting and 14 hours (where appropriate) for the following clinical measures:

- upper and lower lid margin staining
- NIBUT
- TMH
- tear film osmolarity

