### **2.3. Hypotheses**

Primary Hypotheses

For Part 1:

1. Symptomatic subjects will have, on average, statistically significantly, greater upper and lower lid margin staining compared to asymptomatic subjects after 14 hours of lens wear.
2. Symptomatic subjects will have, on average, statistically significantly, shorter NIBUT compared to asymptomatic subjects after 14 hours of lens wear.
3. Symptomatic subjects will have, on average, statistically significantly, lower TMH compared to asymptomatic subjects after 14 hours of lens wear.
4. Symptomatic subjects will have, on average, statistically significantly, greater tear film osmolarity compared to asymptomatic subjects after 14 hours of lens wear.
5. Symptomatic subjects will have, on average, statistically significantly, greater density of white blood cells (visualized by confocal microscopy) in both the upper and lower lid margins compared to asymptomatic subjects after 6 hours of lens wear.

Secondary Hypotheses:

For Part 1 and 2

1. There is a statistically significant relationship with at least one of the five clinical measures (lid margin staining, NIBUT, TMH, tear film osmolarity and density of white blood cells) and subjective comfort measured using VAS grading scales at 14 hours (6 hours for white cells).

Other Hypotheses:

For Part 2:

1. Symptomatic subjects will have, on average, statistically significantly, greater upper and lower lid margin staining compared to asymptomatic subjects after 14 hours of lens wear.
2. Symptomatic subjects will have, on average, statistically significantly, shorter NIBUT compared to asymptomatic subjects after 14 hours of lens wear.
3. Symptomatic subjects will have, on average, statistically significantly, lower TMH compared to asymptomatic subjects after 14 hours of lens wear.
4. Symptomatic subjects will have, on average, statistically significantly, greater tear film osmolarity compared to asymptomatic subjects after 14 hours of lens wear.

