# Clinical Study Protocol

## Johnson & Johnson Vision Care, Inc.

	wearing their habitual lenses	White blood Cell Count			
--	-------------------------------	------------------------	--	--	--

Table 5: Lid Margin Staining – Completed Per-Protocol Population [REDACTED]

LMS (Mean [STD]) **	Eyelid	Strata	
		Asymptomatic N=50	Symptomatic N=32
Baseline	Lower	0.98 (0.95)	1.15 (0.75)
	Upper	0.79 (0.75)	0.68 (0.58)
14-Hours Post Lens Insertion	Lower	1.34 (0.77)	1.47 (0.72)
	Upper	0.74 (0.89)	1.31 (0.87)

N=Number of eyes.

Table 6: Non-Invasive Tear Break-Up Time (NITBUT in Seconds) – Completed Per-Protocol Population [REDACTED]

NIBUT (Mean [STD]) **	Strata	
	Asymptomatic N=25	Symptomatic N=16
Post Lens Insertion	13.19 (8.917)	11.47 (7.035)
14-Hours Post Lens Insertion	9.46 (4.608)	8.34 (4.660)

N=Number of Subjects

\*\*Averaged across three measurements

Table 7: Tear Meniscus Height (TMH) – Completed Per-Protocol Population [REDACTED]

TMH (Mean [STD]) **	Eyelid	Strata	
		Asymptomatic N=50	Symptomatic N=16
Baseline	Lower	0.21 (0.054)	0.21 (0.059)
	Upper	0.16 (0.036)	0.017 (0.034)
Post Lens Insertion	Lower	0.20 (0.056)	0.19 (0.048)
	Upper	0.16 (0.041)	0.15 (0.036)
14-Hours Post Lens Insertion	Lower	0.18 (0.065)	0.14 (0.067)
	Upper	0.14 (0.044)	0.12 (0.030)

N=Number of eyes.

\*\*Averaged across three measurements

Table 8: Tear Film Osmolarity (mOsm/L) – Completed Per-Protocol Population [REDACTED]

TOSM (Mean [STD]) **	Strata	
	Asymptomatic N=25	Symptomatic N=16
Post Lens Insertion	319.52 (75.538)	297.47 (10.899)
14-Hours Post Lens Insertion	301.38 (34.473)	288.41 (58.943)

N=Number of Subjects

\*\*Averaged across two measurements

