# **Clinical Study Protocol**

## **Johnson & Johnson Vision Care, Inc.**

NIBUT or lower TMH, on average, for symptomatic subjects compared to asymptomatic subjects after 14 hours of lens wear will be concluded if the upper limit of the 95% confidence intervals for the Least-squares means is less than 0.

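### The change-from-baseline test in 14.7 item 4 applies one "greater than zero" rule to all four measures, with no sign defined for change; under follow-up minus baseline it is the wrong direction for NIBUT and TMH

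*Combined protocol and SAP*

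**What the plan says.** The hypothesis in 14.7, item 4 for Parts 1 and 2, is that "symptomatic subjects will have a greater change from baseline in all the clinical measures except density of white blood cells". Section 2.3 carries the matching hypothesis. For the analysis, "the response variable will be the change of LMS, NIBUT, TMH, and TOSM from the corresponding baseline", and baseline is dropped as a covariate. Otherwise the steps of the primary analysis are said to apply exactly.

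The strata are compared with a "one-sided 95% CI of least-square means differences (symptomatic - asymptomatic) for the change from baseline". One hypothesis pair is printed for all four measures: H0 is a difference of at most 0 and H_A is a difference above 0. The decision rule is "A statistically greater change, on average, for symptomatic subjects compared to asymptomatic subjects will be concluded if the lower limit" exceeds 0.

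The endpoint in 2.2 (Other Endpoints) reads "Change from baseline and 14 hours and change from fitting and 14 hours", which gives no order of subtraction. The protocol does write an order, follow-up minus baseline, for the neighbouring CLDEQ-8 correlation analysis (14.7 item 3 and the matching objective and hypothesis).

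The primary analysis separates the directions. Section 2.3 states, for example: "Symptomatic subjects will have, on average, statistically significantly, lower TMH compared to asymptomatic subjects after 14 hours of lens wear". In 14.5, H_A for NIBUT and TMH is a difference below 0, and "lower TMH, on average, for symptomatic subjects compared to asymptomatic subjects after 14 hours of lens wear will be concluded if the upper limit" is below 0. LMS and TOSM use the above-0 alternative.

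**The concern.** A one-sided test needs a signed response and a direction that suits it. Item 4 gives one direction for four measures that the protocol expects to move in different ways: in 2.3, symptomatic wearers are expected to have higher LMS and TOSM but lower NIBUT and TMH at 14 hours.

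If change is follow-up minus baseline, a bigger fall is a more negative number. A bigger symptomatic fall in NIBUT or TMH then lies inside item 4's null hypothesis, and a smaller symptomatic fall lies on the side labelled greater change. For two of four measures, in both Parts, the printed rule could not deliver the finding in the expected direction and could deliver the opposite label. If the tail were instead chosen at analysis, the one-sided test would no longer be prespecified.

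**Working it through.** **1. Can any single signed definition make the rule right?** Write D for symptomatic minus asymptomatic mean change. The rule concludes only when the lower limit for D is above 0.

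| Definition of change | Larger symptomatic fall (NIBUT, TMH) | Larger symptomatic rise (LMS, TOSM) |
|---|---|---|
| Follow-up minus baseline | D < 0, rule fails | D > 0, rule works |
| Baseline minus follow-up | D > 0, rule works | D < 0, rule fails |

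Neither order serves all four measures. An absolute change, or a worsening score defined per measure, could fit the rule, but the protocol defines neither.

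**2. Reproducing the plan's own power figures.** The method is a two-sample t test with the noncentral t distribution, 27 per stratum, df = 52 and one-sided 5% (critical value 1.675). The noncentrality is Δ / (σ√(2/27)).

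- NIBUT, Table 11, Δ = -2.1, σ = 3: standard error 0.816, noncentrality 2.57 in absolute value, power 81.4% (stated 81%).
- TMH, Table 12, Δ = -0.04, σ = 0.06: standard error 0.0163, noncentrality 2.45, power 78.0% (stated 78%).

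Two-sided 5% would give 71.4% and 67.2%. The plan's tables are therefore one-sided, with negative Δ for NIBUT and TMH. They concern the 14-hour comparison; no power is stated for item 4.

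**3. TMH under item 4.** From Table 7, lower lid, baseline to 14 hours:

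- Asymptomatic: 0.18 - 0.21 = -0.03
- Symptomatic: 0.14 - 0.21 = -0.07
- D = -0.07 - (-0.03) = -0.04

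The symptomatic fall is the larger one, and D lies inside item 4's null. The documents give no SD of change, so I assume 0.05 to 0.08. The 14-hour SDs in Table 7 are 0.065 and 0.067.

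| True D | SD of change | Rule as written (> 0) | Direction corrected (< 0), one-sided 5% | Two-sided 95% interval wholly below 0 |
|---|---|---|---|---|
| -0.04 | 0.05 | 0.0003% | 89.5% | 82.2% |
| -0.04 | 0.066 | 0.006% | 71.0% | 58.9% |
| -0.04 | 0.08 | 0.03% | 56.7% | 43.8% |

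Each of the four means is rounded to ±0.005, so D could lie between -0.02 and -0.06. At -0.02 with SD 0.08 the figures are 0.54% as written and 23.0% corrected. At -0.06 with SD 0.05 the corrected figure is 99.7%.

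**4. What the other historical tables show.**

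- NIBUT (Table 6, fitting to 14 hours; no pre-lens baseline is tabulated): asymptomatic 9.46 - 13.19 = -3.73 s, symptomatic 8.34 - 11.47 = -3.13 s, D = +0.60 s. This is not a lost finding. It is a smaller symptomatic fall that the rule would count toward greater change.
- TOSM (Table 8, also fitting to 14 hours): asymptomatic 301.38 - 319.52 = -18.14, symptomatic 288.41 - 297.47 = -9.06, D = +9.08. Both strata fell, so a positive D here means a smaller decrease.
- LMS, upper lid (Table 5, baseline to 14 hours): asymptomatic 0.74 - 0.79 = -0.05, symptomatic 1.31 - 0.68 = +0.63, D = +0.68. With the subtraction reversed D would be -0.68 and the rule would miss it.

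**The case against.** The strongest reply is that 2.3 gives directions for 14-hour levels, whereas item 4 speaks only of greater change. Lower NIBUT at 14 hours need not mean a larger fall, since symptomatic wearers may start lower (11.47 against 13.19 s after insertion in Table 6). If greater change means size of change, the above-0 rule is coherent. The first part stands: the expected direction of change is an inference. The second would need an absolute-value response, which the protocol does not state and which is a different variable from the one named.

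Section 14.1 leaves further detail to a stand-alone SAP, which is not among the documents and may define the sign. That lowers the practical risk. However, the hypothesis pair and decision rule are already printed in the protocol, and 14.10 says the analysis will follow these sections.

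The magnitude is soft. The SD of change is assumed and a plain t test stands in for the mixed model. Table 7 labels its N as eyes (50 and 16) although Table 4 lists 25 and 16 completers. The NIBUT and TOSM contrasts run from fitting rather than baseline and are small against the spread of the data. These points are fair. The size is an illustration and those two contrasts only show how the rule would label such results; the argument about the sign does not depend on any of them.

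Finally, this is one of the other hypotheses, 14.4 sets an error rate only for primary and secondary ones, and the estimate and its standard error are the same whichever tail is used. That is right, and it limits the severity.

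**Conclusion.** The concern holds. Item 4 states a single directional rule that no single signed definition of change can make correct for all four measures. Under the only subtraction order the protocol writes, the rule is wrong for NIBUT and TMH: whenever the estimated symptomatic fall is the larger, the lower limit cannot exceed 0. The small probabilities above are the chance that sampling error reverses the observed sign.

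For TMH the cost is a success probability of 0.03% or less instead of 57% to 90%, given a true difference in change of -0.04, an SD of change of 0.05 to 0.08 and 27 per stratum. Allowing for rounding of the means, it is at most about 0.5% against 23% to 99.7%. For NIBUT the historical data show no lost finding, only the risk of a misleading label.

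The defect is confined to an other hypothesis, in both Parts. The primary tests in 14.5, the sample size and data collection are untouched. It should be corrected before the analysis.

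**What to change.** In 14.7 item 4, define change as the 14-hour value minus baseline and state the direction for each measure:

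- **NIBUT and TMH:** H0: μ_S - μ_A ≥ 0 against H_A: μ_S - μ_A < 0. Conclude a greater decrease in symptomatic wearers if the upper limit is below 0, as in 14.5.
- **LMS and TOSM:** keep H_A: μ_S - μ_A > 0 with the lower limit above 0, but word the conclusion as a greater increase (or smaller decrease).

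An alternative is to use two-sided 95% intervals for all four measures and report the direction. This is simpler but costs some power: 44% to 82% rather than 57% to 90% in the TMH illustration.

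Align the endpoint in 2.2 and the hypothesis in 2.3 with the definition, and carry the same text into the SAP before database lock. The cost is one definition, one extra hypothesis pair and matching wording in those places. No data or sample-size change is needed.

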### **14.8. Interim Analysis**

There will not be an interim read performed on this study.

### **14.9. Procedure for Handling Missing Data and Drop-Outs**

Missing or spurious values will not be imputed. The count of missing values will be included in the summary tables and listings.

Subject dropout is expected to be one of the main reasons of missing data in this clinical trial. Past clinical trials don't provide the evidence that subject dropout is systematic or not-at-random. To evaluate the impact of missing data, sensitivity analysis will be conducted using multiple imputation methods if the proportion of subject dropout is greater than the 15%. The SAS/STAT procedures PROC MI and PROC MIANALYZE will be utilized with a parametric regression method used to make at least 50 imputations.

### **14.10. Procedure for Reporting Deviations from Statistical Plan**

The analysis will be conducted according to that specified in above sections. There are no known reasons for which it is planned to deviate from these analysis methods. If for any reason a change is made, the change will be documented in the study report along with a justification for the change.

## **15. DATA HANDLING AND RECORD KEEPING/ARCHIVING**

### **15.1. Electronic Case Report Form/Data Collection**

The data for this study will be captured on electronic case report forms (eCRFs) using an EDC system (Bioclinica). An authorized data originator will enter study data into the eCRFs using the EDC system. Data collected on equipment that is not captured in EDC will be formatted to the specification of the JJVC database manager and sent to JJVC for analysis. Data generated from post hoc measurements (e.g. tear meniscus height, lid wiper image analysis, tear film cytokines, etc.) will be collected on specific Microsoft Office Excel format worksheets at the clinical site and at the completion of the analysis transferred to JJVC biostatistician for data analysis in such format.

The clinical data will be recorded on dedicated eCRFs specifically designed to match the study procedures for each visit. Once completed, the eCRFs will be reviewed for accuracy and completeness and signed by the Investigator. The sponsor or sponsor's representatives will be

# **Clinical Study Protocol**

## **Johnson & Johnson Vision Care, Inc.**

authorized to gain access to the subject recordation for the purposes of monitoring and auditing the study.

Edit checks, electronic queries, and audit trails are built into the system to ensure accurate and complete data collection. Data will be transmitted from the clinical site to a secure central database as forms are completed or updated, ensuring information accuracy, security, and confidentiality. After the final database lock, the Investigator will be provided with Individual Patient Profiles (IPP) including the full audit trail on electronic media in PDF format for all of the study data. The IPP must be retained in the study files as a certified copy of the source data for the study.

The content and structure of the eCRFs are compliant with ISO14155:2011.

### **15.2. Subject Record**

At a minimum, subject record should be available for the following:

- subject identification
- eligibility
- study identification
- study discussion
- provision of and date of informed consent
- visit dates
- results of safety and efficacy parameters as required by the protocol
- a record of all adverse events
- follow-up of adverse events
- medical history and concomitant medication
- test article receipt/dispensing/return records
- date of study completion
- reason for early discontinuation of test article or withdrawal from the study, if applicable

The subject record is the eCRF or an external record. The author of an entry in the subject record must be identifiable. The first point of entry is considered to be the source record.

Adverse event notes must be reviewed and initialed by the Investigator.

## **16. DATA MANAGEMENT**

### **16.1. Access to Source Data/Document**

The Investigator/Institution will permit trial-related monitoring, audits, IEC/IRB review and regulatory inspection(s) by providing direct access to source data/documents. Should the clinical site be contacted for an audit by an IEC/IRB or regulatory authority, JJVC must be contacted and notified in writing within 24 hours.

# **Clinical Study Protocol**

## **Johnson & Johnson Vision Care, Inc.**

### **16.2. Confidentiality of Information**

Information concerning the investigational product and patent application processes, scientific data or other pertinent information is confidential and remains the property of JJVC. The Investigator may use this information for the purposes of the study only. It is understood by the Investigator that JJVC will use information developed in this clinical study in connection with the development of the investigational product and therefore may disclose it as required to other clinical investigators and to regulatory agencies. In order to allow the use of the information derived from this clinical study, the Investigator understands that he/she has an obligation to provide complete test results and all data developed during this study to the Sponsor.

### **16.3. Data Quality Assurance**

Steps will be taken to ensure the accuracy and reliability of data, include the selection of qualified investigators and appropriate clinical sites and review of protocol procedures with the Principal Investigator. The Principal Investigator, in turn, must ensure that all Sub-Investigators and clinical site personnel are familiar with the protocol and all study-specific procedures and have appropriate knowledge of the study article.

Training on case report form completion will be provided to clinical site personnel before the start of the study. The Sponsor will review case report forms for accuracy and completeness remotely during the conduct of the study, during monitoring visits, and after transmission to data management. Any data discrepancies will be resolved with the Investigator or designee, as appropriate.

Quality Assurance representatives from JJVC may visit clinical sites to review data produced during the study and to assess compliance with applicable regulations pertaining to the conduct of clinical trials. The clinical sites will provide direct access to study-related source data/documents and reports for the purpose of monitoring and auditing by JJVC and for inspection by local and regulatory authorities.

## **17. MONITORING**

The study monitors will maintain close contact with the Principal Investigator and the Investigator's designated clinical site personnel. The monitor's responsibilities will include:

- Ensuring that the investigation is being conducted according to the protocol, any subsequent amendments, and regulatory requirements are maintained
- Ensuring the rights and wellbeing of subjects are protected
- Ensuring adequate resources, including facilities, laboratories, equipment, and qualified clinical site personnel
- Ensuring that protocol deviations are documented with corrective action plans, as applicable
- Ensuring that the clinical site has sufficient test article and supplies
- Clarifying questions regarding the study
- Resolving study issues or problems that may arise

